#### 10.5. Retention of Records

In accordance with applicable regulatory requirements, following closure of the study, the Investigator will maintain a copy of all site study records in a safe and secure location in the original format until at least 2 years after the last approval of a marketing application or at least 2 years have elapsed since the formal discontinuation of clinical development of the SM.

Essential documents include:

- Signed informed consent documents for all subjects
- Subject identification code list, screening log (if applicable) and enrollment log
- Record of all communications between the Investigator and the IRB
- Copies of CRFs and of documentation of corrections for all subjects
- SM accountability records
- All other source documents (subject medical records, hospital records, laboratory records, etc.)
- All other documents as listed in Section 8 of the ICH E6 Guideline for GCP (Essential Documents for the Conduct of a Clinical Trial)

Normally, these records will be held in the Investigator's archives. If the Investigator is unable to meet this obligation, he or she must ask the sponsor for permission to make alternative arrangements. Details of these arrangements should be documented.

#### 10.6. Auditing Procedures

In addition to the routine monitoring procedures, the Sponsor's Corporate Quality Assurance department may conduct audits of clinical research activities in accordance with the Sponsor's SOPs to evaluate compliance with the principles of ICH GCP and all applicable local regulations. A government regulatory authority may also wish to conduct an inspection (during the study or after its completion). If an inspection is requested by a regulatory authority, the Investigator must inform the Sponsor immediately that this request has been made.

#### **10.7.** Publication of Results

Any presentation or publication of data collected as a direct or indirect result of this trial will be considered as a joint publication by the Investigator(s) and the appropriate personnel at the Sponsor's site. Authorship will be determined by mutual agreement. The study is being conducted as part of a multicenter clinical trial. As stipulated in the protocol, data from all such sites shall be pooled and analyzed. All manuscripts, abstracts or other modes of presentation arising from the results of the study must be reviewed and approved in writing by the Sponsor, at least ninety (90) days prior to submission for publication or presentation. No publication or presentation with respect to the study shall be made until any Sponsor comments on the proposed publication or presentation have been addressed to the Sponsor's satisfaction.

The detailed obligations regarding the publication of any data, material results, or other information, generated or created in relation to the study shall be outlined in the agreement between each Investigator and the Sponsor (or designee).

### **10.8. Disclosure and Confidentiality**

The contents of this protocol and any amendments and results obtained during the course of this study will be kept confidential by the Investigator, the Investigator's staff, and IRB and will not be disclosed in whole or in part to others or used for any purpose other than reviewing or performing the study without the written consent of the Sponsor. No data collected as part of this study will be utilized in any written work, including publications, without the written consent of Sponsor. These obligations of confidentiality and non-use shall in no way diminish such obligations as set forth in the Confidentiality Agreement between the Sponsor and the Investigator.

All persons assisting in the performance of this study must be bound by the obligations of confidentiality and non-use set forth in the Confidentiality Agreement between the Investigator and Sponsor (provided by the Sponsor).

#### **10.9.** Discontinuation of Study

The Sponsor reserves the right to discontinue the study for medical or administrative reasons at any time. Reimbursement for expenses covering subjects, laboratory tests, and other professional fees will be made. The Investigator will refund the excess of payments made in advance.

The Investigator reserves the right to discontinue the study should his/her judgment so dictate. In such an event, final settlement of the grant-in-aid will be adjusted pro rata, and the Investigator will refund the excess of payments made in advance. The Investigator will notify the IRB in case of study discontinuation. Study records must be retained as noted above.

### 12. APPENDICES

# 12.1. Conners' Adult ADHD Rating Scale (CAARS)

# 12.1.1. Investigator-Report

[figure not shown]
# 12.1.2. Self-Report

[figure not shown]
# 12.2. Clinical Global Impression (CGI) Scale

# 12.3. Columbia-Suicide Severity Rating Scales (C-SSRS)

## 12.3.1. Baseline

[figure not shown]

# 12.3.2. Since Last Visit

Supernus Pharmaceuticals, Inc.CONFIDENTIALSPN-812V - 812P201version 2.0

Supernus Pharmaceuticals, Inc. SPN-812V - 812P201

Supernus Pharmaceuticals, Inc. SPN-812V - 812P201

### LIST OF ABBREVIATIONS

ADHD Attention Deficit Hyperactivity Disorder

AE adverse event

ALT alanine aminotransferase ANOVA analysis of variance

AST aspartate aminotransferase
ATC Anatomical-Therapeutic-Chemical

AUC area under the plasma concentration versus time curve

BUN blood urea nitrogen

CAARS Conners' Adult ADHD Rating Scale

CAADID Conners' Adult ADHD Diagnostic Interview for DSM-IV

CFR Code of Federal Regulations
CGI Clinical Global Impression

CGI-S Clinical Global Impression – Severity of Illness
CGI-I Clinical Global Impression – Global Improvement

CL/F apparent oral clearance CRA Clinical Research Associate

CRF Case Report Form

C-SSRS Columbia-Suicide Severity Rating Scales

CRO Contract Research Organization

DSM-IV-TR Diagnostic and Statistical Manual of Mental Disorders – Text Revision

ECG electrocardiogram

FOCP Females of Childbearing Potential FDA Food and Drug Administration

GCP Good Clinical Practice

GGT gamma-glutamyl transpeptidase

HR Heart rate

ICF Informed Consent Form

ICH International Conference on Harmonization

IRB Institutional Review Board

ITT intent to treat LNH Low, normal, high

MedDRA Medical Dictionary for Regulatory Activities

PK pharmacokinetic

PK-PD pharmacokinetic-pharmacodynamic

PO orally

PR Interval from the P wave (atrial contraction or depolarization) to the onset of

the Q wave in the measurement of electrical activity of the myocardium

QRS QRS complex refers to ventricular depolarization in the measurement of

electrical activity of the myocardium

QT Interval from ventricular depolarization and repolarization in the measurement

of electrical activity of the myocardium

QTc QT, corrected

QTcF QT corrected using Fridericia's method

RBC red blood cell

SAE serious adverse event SM study medication SOC System Organ Class

SOP Standard Operating Procedure

Supernus Pharmaceuticals, Inc. CONFIDENTIAL 09 FEB 2011 Statistical Analysis Plan (Protocol: 812P201) FINAL 2.0 Page 6 of 26

**TEAE** 

treatment-emergent adverse event three times per day upper limit of normal TID ULN

US United States **WBC** white blood cell

World Health Organization Drug Dictionary WHO DD

### 1. INTRODUCTION

The purpose of this statistical analysis plan (SAP) is to reasonably ensure that the tables, data listings and figures which will be produced, and statistical methodologies that will be used, are complete and allow for the arrival at valid conclusions regarding the study objectives. In the development of this SAP, the following documents were used:

- The Final Protocol 812P201, Version 2.0, 30 June 2010
- eCRF Screen Shots Phase 1 (Received from Emphusion on 22 June 2010)
- eCRF Screen Shots Phase 2 (Received from Emphusion on 08 July 2010)
- eCRF and Database Specifications, Version 1.2 (24 August 2010).

### 2. STUDY OBJECTIVES

### 2.1 PRIMARY OBJECTIVE

The primary objective is to evaluate the safety of SPN-812V in adults with ADHD.

### 2.2 SECONDARY OBJECTIVES

The secondary objectives of this study are:

- To determine the efficacy and of SPN-812V in adults with ADHD
- To explore the single dose and steady state pharmacokinetics of SPN-812V in adults with ADHD.

### 3. DESIGN OF THE STUDY

### 3.1 STUDY DESIGN

This will be a multicenter, randomized, double-blind, placebo-controlled, parallel group study of the safety and efficacy of SPN-812V in adults with ADHD. The target subjects are male or female adults aged 18 to 64 years, inclusive, with a diagnosis of ADHD. A total of fifty subjects will be enrolled at approximately 5 sites in the US. Subjects will be randomized (1:1) to one of two treatment groups, SPN-812V or placebo.

The study will consist of a Screening Period (within 14 days prior to randomization) and a Dosing Period of 6 weeks. The total subject duration in the study will be up to 8 weeks as illustrated in Figure 1.

[figure not shown]

Figure 1 Study Schematic

### 3.1.1 Screening

Screening will take place within 14 days prior to randomization to determine subjects' eligibility to participate in the study. Screening procedures will be performed to determine each subject's eligibility to participate in the study and may be carried out over more than one visit during the Screening Period.

### 3.1.2 Dosing Period

Subjects who meet the requirements for study participation will be randomized and proceed to the Dosing Period which will last 6 weeks. Approximately 50 subjects will be randomized at a 1:1 ratio, using a centralized randomization system, to either SPN-812V or placebo. The first dose of SM should be taken the morning after the randomization visit. Subjects who do not tolerate the starting dose will be discontinued from the study.

The first dose of SM should be taken the morning after the randomization visit. Subjects will receive treatment at the 150 mg/day starting dose for one week. Subjects who do not tolerate the starting dose will be discontinued from the study.

Subjects who tolerated the starting dose will then be titrated to receive a study dose of 2x50 mg TID (300mg/day) and continue this treatment regimen for five weeks. Subjects who, after titration to the study dose, do not tolerate treatment at 300 mg/day, will be allowed, at any time, to down-titrate the dose to the 150 mg/day starting dose and continue treatment at the same dose until completion of the study. Subjects will return to the investigational site once a week to undergo safety and efficacy evaluations and to have SM compliance checked.

Subjects who have consented to participate in the optional PK sub study will be given a diary at Visit 7 on which to record time of SM doses taken prior to Visit 8. Subjects who are participating in the optional PK sub study will be given all efficacy assessments prior to blood draws or dosing on the PK day. For subjects not participating in the optional PK sub study, their last dose will be taken the evening before the End of Study Visit (Visit 8).

### 3.1.3 End of Study Visit/Early Termination

At the end of Visit 8, or prior to early discontinuation, subjects will undergo end of study assessments. AEs will be monitored, and safety tests and efficacy scales will be administered unless assessments were performed earlier in the visit. Subjects will return any unused capsules and undergo safety and efficacy evaluations if not already performed as part of that visit.

### 3.1.4 Pharmacokinetic Sampling

On the final visit, there is an optional PK day. All subjects who wish to participate will be dosed with active SM after an overnight fast and after all efficacy assessments are completed, Blood will be drawn for quantitative PK analysis according to the following schedule (all times  $\pm$ -30 minutes): Pre-dose and ½, 1, 2, 3, 4, 5, and 6 hours post-dose.

### 3.2 SAMPLE SIZE CONSIDERATION

Approximately 50 subjects (approximately 25 per treatment group) will be randomized in the study. The sample size is not based on any statistical considerations, but it was judged adequate to provide safety, PK, and efficacy information for a proof-of-concept study.

### 3.3 RANDOMIZATION PROCEDURE

The randomization for this study will be managed centrally by an IVRS vendor; specific instructions to conduct subject randomization will be provided in a separate document to all investigational sites, along with site staff access to the system.

Upon admission to the study, subjects will be assigned a 4-digit screening number, in the order that they are entered. Subjects who subsequently meet all eligibility criteria will be assigned a 6-digit randomization number. The first 3 digits will refer to the site, and the last 3 will refer to the subject-specific number, which will be assigned according to the randomization scheme.

#### 3.4 SCHEDULE OF VISITS AND PROCEDURE

All subjects who are randomized and take any SM will be followed according to the protocol, unless consent for follow-up is withdrawn. The Sponsor, or the Sponsor's designee, must be notified of all deviations from the protocol visits or procedures and these procedures, if applicable, will be rescheduled or performed at the nearest possible time to the original schedule.

The exhibit on the next page presents the schedule of visits and procedures for the study (Table 1).

Table 1. Schedule of Visits and Procedures

Study Phase	Communication Devicts	Dose Treatment Period		End of
	Screening Period	(Visit windo	(Visit window +/- 2 days)	
Activity	Visit 1 Up to 14 Days Prior to Visit 2	Visit 2	Visits 3 – 8	
Informed Consent a	X			
Medical and Psychiatric History and Demographics	X			
Physical Exam	X			X
ECG (12-lead)	X		X c	X
Vital Signs d	X	X	X	X
Hematology	X			X
Urinalysis and drug screen	X			X
CYP2D6 Enzyme Activity Screening	X			
Serum Chemistry	X			X
Serum Pregnancy Test (for FOCP only)	Х			X
Urine Pregnancy Test (for FOCP only)		х		
CAADID	X			
CGI	X	X	X	X
C-SSRS	X	X	X	X
CAARS e		X	X	X
Concomitant Medication	X	X	X	X
Randomization		X		
SM Dispensed		X	X	
SM Diary Dispensed			X f	
Optional SM Administered On-Site g			X	
Optional PK Blood Sampling			X h	
Adverse Events			X	X i

- a To be obtained prior to any study procedures being performed.
- b To be performed at the end of Visit 8 (unless done previously during Visit 8), or at early discontinuation.
- c At Visit 4 only
- d Heart rate, seated blood pressure, temperature, and respiratory rate will be measured at every visit. The vital signs readings will be performed within approximately 10 minutes prior to the scheduled blood draws, where applicable. Height will be taken at screening and weight will be assessed at each visit.
- e CAARS self-report done only at Visits 2 and 8, CAARS investigator-report done at Visits 2-8
- f At Visit 7 to record SM taken prior to Visit 8. Diary to be collected at Visit 8.
- Dose to be administered on-site after the pre-dose draw and an overnight fast at Visit 8; subjects may eat 2 hours after dosing.
- h At Visit 8, subjects who wish to participate will be dosed after an overnight fast and have a series of PK samples drawn. Samples will be taken pre-dose, and at Hours ½, 1, 2, 3, 4, 5, and 6.
- i Any subject who experiences an adverse event (whether serious or non-serious) or has a clinically significant abnormal laboratory test value(s) will be followed by the Investigator at appropriate intervals based on the severity and nature of the event, until resolved, or when the condition is assessed as stable, causality other than the SM has been found, or the subject is referred to another health care professional.

### 3.5 EFFICACY MEASURES

### 3.5.1 Primary Efficacy Measure

The primary efficacy measure is the investigator-rated CAARS Total ADHD Symptom Score which is the sum of the Inattention and Hyperactivity/Impulsivity subscales (18 items rated on 4-point scale: 0, 1, 2 and 3).

### 3.5.2 Secondary Efficacy Measures

The secondary efficacy measures are:

- Clinical Global Impression Improvement (CGI-I)
- Self-rated Conners' Adult ADHD Rating Scale (CAARS). This assessment will be administered at study Visits 2 and 8.

#### 3.6 SAFETY MEASURES

Safety measures during the study will consist of AE and SAE monitoring, clinical laboratory tests, vital signs, physical examinations, and 12-lead ECGs.

#### 3.6.1 Adverse Events

For subjects who receive SM, all AEs will be collected starting from providing informed consent for study participation. All AEs will be collected on the AE Case Report Form (CRF). SAEs will be reported if the Investigator believes the event is at least possibly related to SM. Investigator will assess the severity and the causality of AEs.

A cluster of signs and symptoms that results from a single cause should be reported as a single AE (e.g., fever, elevated WBC, cough, abnormal chest X-ray, etc. can all be reported as "pneumonia").

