## 9.4.4.1.1. Reporting of Adverse Events

All subjects will be closely questioned regarding the occurrence of AEs.

For subjects who receive SM, all AEs (learned of through spontaneous reports or subject interview) will be collected starting from the first dose of SM until the end of the study. All AEs will be collected on the AE Case Report Form (CRF). All SAEs will be reported to the Sponsor.

A cluster of signs and symptoms that results from a single cause may be reported as a single AE (e.g., fever, elevated WBC, cough, abnormal chest X-ray, etc. can all be reported as "pneumonia").

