## 9.4.4.2.1. Reporting of SAEs

All SAEs must be reported to the Safety Contact person(s) within 24 hours of first becoming aware of the SAE. The Investigator must complete an SAE Form, including a detailed description of the SAE and all other information available (e.g., hospital records, autopsy reports and other relevant documents). The Investigator must inform the IRB about such AEs in accord with ICH guidelines and the practices of the governing IRBs (Section 5.1.).

Follow-up information, or new information available after the initial report, should be actively sought and reported to the Sponsor as it becomes available using the SAE Form.

Safety Contact persons and all contact information are listed in the Site Manual and/or Regulatory Binder provided to each investigational site.

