## 9.7.1.4.1. Adverse Events

AEs will be classified into standardized medical terminology from the verbatim description (Investigator term) using the Medical Dictionary for Regulatory Activities (MedDRA). AEs will be presented in the summary tables by preferred term nested within System Organ Class (SOC). Verbatim description and all MedDRA level terms, including the lower level terms, for all AEs will be contained in the subject data listings.

Data for AEs will be analyzed using the treatment-emergent signs and symptoms (TESS) philosophy. TESS are defined as AEs that:

- emerge during treatment, having been absent at pretreatment, or
- reemerge during treatment, having been present at pretreatment but stopped prior to treatment, or
- worsen in severity during treatment relative to the pretreatment state, when the AE is continuous.

Only treatment-emergent AEs (TEAEs) from the study will be summarized in tables. TEAEs will be summarized by presenting, for each treatment group, the incidence of AEs. The incidence of TEAEs will be based on the numbers and percentages of subjects with TEAEs. Although a MedDRA term may be reported more than once for a subject, that subject will be counted only once in the incidence count for that MedDRA term.

Separate TEAE incidence tables will be presented for the Baseline and Randomization Period, Dose Treatment Period, and combined Baseline and Randomization and Dose Treatment Periods. For the combined Baseline and Randomization and Dose Treatment Periods, the incidence of TEAEs will also be presented by highest severity reported, closest relationship to SM reported, and the dose of SM at first occurrence. For treatment-related TEAEs only, i.e., those TEAEs classified as possibly or definitely related to SM, the incidence rates will also be summarized as described previously for all TEAEs. Listings (and tabular summaries, if warranted) of deaths, other SAEs, and other significant AEs, including AEs resulting in treatment discontinuation, will be provided.

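### The SAP text names three of the six TEAE displays the protocol requires, none by period or dose, and its SAE-reporting and AE-collection wording conflicts with the protocol

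*SAP*

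**What the plan says.** Protocol 9.7.1.4.1 specifies the adverse-event tables in three steps. It begins with period: "Separate TEAE incidence tables will be presented for the Baseline and Randomization Period, Dose Treatment Period", and the two periods combined. For the combined period it adds incidence by highest severity, "closest relationship to SM reported, and the dose of SM at first occurrence". For treatment-related TEAEs (possibly or definitely related), "the incidence rates will also be summarized as described previously for all TEAEs".

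SAP 6.1.1 names four tables: overall incidence (14.3.1.1.1), incidence by system organ class and preferred term (14.3.1.1.2), the same by relationship (14.3.1.1.3), and the same by severity (14.3.1.1.4). SAP 6.1.2 repeats these four by sex, race and ethnicity. SAP 6.1.3 provides listings of deaths, SAEs and other significant events, including those leading to discontinuation, dose reduction or interruption. SAP 4.5 summarizes compliance and exposure separately for the starting-dose week, for the later dosing phase and for both combined.

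On SAE reporting, SAP 3.6.1 says "SAEs will be reported if the Investigator believes the event is at least possibly related to SM". Protocol 9.4.4.1.1 says "All SAEs will be reported to the Sponsor", and Protocol 9.4.4.2.1 says "All SAEs must be reported to the Safety Contact person(s) within 24 hours of first becoming aware of the SAE".

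On the start of collection, SAP 3.6.1 says "For subjects who receive SM, all AEs will be collected starting from providing informed consent for study participation". Protocol 9.4.4.1.1 says that AEs "will be collected starting from the first dose of SM until the end of the study", and Protocol 9.4.1.2 also places the start after the first dose.

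**The concern.** The synopsis states the primary endpoint as safety after six weeks on either dose, and the Introduction describes evaluating safety and tolerability at 150 or 300 mg/day. The protocol's period tables and dose-at-first-occurrence table are the displays that would show at which dose level events began. If the SAP is programmed as its text reads, exposure would be split by dosing phase but adverse events would not. A reader of the report could not set events in the starting-dose week against exposure in that week.

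Protocol 9.7.1 says the SAP will describe the protocol's analyses in more detail. Leaving out required displays is a change from the protocol, and a change should be recorded.

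The SAE sentence is a separate matter. Two study documents state different reporting rules, one conditional on the investigator's causality judgment and one not. They also give different start points for AE collection.

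**Working it through.** The documents give no figure to reproduce. The check counts the displays in Protocol 9.7.1.4.1 against the tables named in SAP 6.1.1 and 6.1.2.

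| Display required for all TEAEs | Named in the SAP text? |
|---|---|
| 1. Incidence, Baseline and Randomization Period | No |
| 2. Incidence, Dose Treatment Period | No |
| 3. Incidence, both periods combined | Yes, Table 14.3.1.1.2 |
| 4. Combined, by highest severity | Yes, Table 14.3.1.1.4 |
| 5. Combined, by closest relationship | Yes, Table 14.3.1.1.3 |
| 6. Combined, by dose at first occurrence | No |

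- Required: 3 period tables + 3 combined-period breakdowns = 6.
- Named: 3. Not named: 6 − 3 = 3. Table 14.3.1.1.1 (overall incidence) is not one of the six.
- All AE tables named in the SAP: 4 overall + 3 variables × 4 tables = 4 + 12 = 16. None is by separate period or by dose.

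*Treatment-related TEAEs.* No separate set is named. Table 14.3.1.1.3 covers part of the requirement: combined-period incidence and the relationship categories can be read from it. It gives no breakdown of related events by period, severity or dose.

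*Is the change recorded?* SAP section 8 is titled as changes from the protocol, but its text addresses only changes made after database lock. The revision history in SAP section 12 lists two items, in sections 4.2 and 5.4. Neither place mentions the AE tables.

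*What a dose table could show.* The schedule is one week at 150 mg/day followed by five weeks at 300 mg/day. A completer who is not down-titrated therefore spends 1/6 = 17% of dosing time at 150 mg/day, always in the first week. Dose at first occurrence is confounded with time on treatment.

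*SAE rule and collection start.*

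| Item | SAP 3.6.1 | Protocol |
|---|---|---|
| SAEs reported | If at least possibly related | All, no causality condition (9.4.4.1.1, 9.4.4.2.1) |
| AE collection starts | Informed consent | First dose (9.4.4.1.1, 9.4.1.2) |

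The effect on the analysis can be traced within the SAP. All AEs go on the case report form (3.6.1), and SAEs are listed without a causality filter (6.1.3). SAP 6.1.1 tabulates only events that occur or worsen after the first dose, so the different collection start does not change which events its tables count.

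**The case against.** The strongest defense is that the practical effect is small. Sites follow the protocol, and SAP 3.4 itself says subjects are followed according to it. The pooled any-dose comparison with placebo in the synopsis is still covered. AEs leading to dose reduction are listed (SAP 6.1.3), and Table 14.1.4.2 counts subjects reduced in dose. The missing displays also overlap: for anyone not down-titrated, a week-1 table and a later-period table already separate events by dose. All of this stands, and it limits the size of the point. It does not remove it, because the listings and Table 14.1.4.2 give no incidence by dose at onset, and the SAP names neither the period tables nor the dose table.

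A reader might infer more than the documents support:

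- *That the tables will not be produced.* SAP section 10 puts the shells in separate documents, which were not available. The finding is limited to what the SAP text names.
- *That unrelated SAEs drop out of the analysis.* The SAE listing has no causality filter, so the conflict concerns a reporting rule only.
- *A larger count of missing tables.* If the treatment-related requirement means all six displays again, the total is 6 + 6 = 12. How many are then unnamed depends on that reading and on how much credit Table 14.3.1.1.3 receives. Only the count of 3 of 6 for all TEAEs is firm.
- *That SAP 4 and 6 conflict over down-titrated subjects.* The trial has two arms, SPN-812V and placebo. Analysis by treatment actually received reads naturally as active versus placebo, which is compatible with keeping down-titrated subjects in the 300 mg/day group.
- *That AEs with unknown onset are assigned to the 150 mg/day week.* The example in SAP 6.1.1 speaks of onset time, and most naturally means an event on the first-dose day with no clock time. The wording is loose, but that consequence is not established.

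**Conclusion.** The point holds and should be fixed. The SAP text names 3 of the 6 all-TEAE displays required by Protocol 9.7.1.4.1. The two single-period tables and the dose-at-first-occurrence table are not named, there is no separate treatment-related set, and neither SAP section 8 nor the revision history records a change. As the text stands, no AE incidence table distinguishes events at 150 mg/day from events at 300 mg/day in a trial whose primary endpoint is safety at either dose.

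SAP 3.6.1 also contradicts the protocol on which SAEs are reported and on when AE collection starts. No SAE count or TEAE count is shown to change as a result.

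The conclusion rests on the SAP text alone, since the shells were not seen. The count of six assumes that the three periods and the three combined-period breakdowns are separate displays, which is how the protocol lists them.

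**What to change.** - **SAP 6.1.1:** name the TEAE incidence tables for each period, using the split already defined in SAP 4.5; the table by dose at first occurrence; and the treatment-related TEAE summaries. Alternatively, record in SAP section 8 that they are removed, and why.
- **Dose table:** present it descriptively. Dose is confounded with time on treatment, so it should not be read as a comparison of 150 with 300 mg/day.
- **SAP 3.6.1:** reconcile the SAE-reporting sentence and the start of AE collection with Protocol 9.4.4.1.1 and 9.4.4.2.1.

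The cost is a few SAP sentences and a small number of extra descriptive tables. No protocol amendment is needed to add the tables, because the protocol already asks for them. This assumes the case report form holds AE onset dates and dose-change dates; the eCRF specifications were not available to confirm it.
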